8.1 Screening failures

A summary of reasons for screening failure will be presented for the TOS.

8.2 **Protocol deviations**

Overall important PDs will be summarized by trial, country, site and subject level. Furthermore, the important PDs will be summarized by the subject level deviations and treatment. A listing with all important PDs will be presented.

8.3 Subject disposition

Subject disposition will be summarised by number and percentage of subjects screened, randomised and not treated, randomised and treated, included in the analysis sets, completed trial, withdrawal from the trial, reason of withdrawal of trial, completed IMP, discontinued IMP, and reason for IMP discontinuation by treatment group and total. Some endpoints will be also summarised by year. In addition, the reasons for discontinuation of IMP following the estimand framework will be summarised by treatment groups and total.

IMP discontinuations over time by different reasons will be visualised by a band plot showing proportions on treatment, having discontinued treatment due to AE, withdrawal by subject, and all other reasons (pooled).

8.4 Baseline characteristics

Demographic variables (age, sex, race, country) will be summarised by treatment and total groups.

Statistical analysis plan	Date:	27-Oct-2023	AL
Trial ID: SU-G-01	Version:	1.0	
EudraCT No.: 2020-000455-12	Status:	Final	
CONFIDENTIAL	Page:	34 of 47	

Baseline characteristics (including baseline asthma status, inhaled corticosteroid use, duration of grass pollen allergy and mono/poly sensitized) are summarised by treatment groups.

In separate tables, SPT test results (including actual wheel size and results and whether subjects are mon/poly sensitised), FEV_1 , percentage of predicted FEV_1 and IgE are summarised by treatment groups.

8.5 Pollen counts

Pollen season definitions are provided in Section 9.1. Pollen counts will be summarised by treatment group and total. Pollen counts will be weighted by the number of subjects in each pollen station and divided by the number of subjects in the trial. In addition, lengths of EGPS and for each year will be summarised. Lengths of EGPS will also be weighted as pollen counts.

8.6 Medical history

Medical history will be summarised by treatment groups. Medical history of allergic rhinitis, conjunctivitis, asthma, atopic dermatitis and food allergy are summarised by treatment groups.

8.7 **Prior and concomitant therapy**

Prior and concomitant medication will be summarised by treatment groups.

9 Supporting documentation

9.1 Definition of pollen seasons

Each trial site was allocated to a pollen station. The start and stop dates of the grass pollen seasons will be based on the daily pollen counts as defined in Table 10. The pollen EGPS dates will be within a period of expected pollen season defined trial protocol (see Trial Protocol, Appendix 5: Expected grass pollen season).

Start date of EGPS	The first day of 3 consecutive days with (non-missing) pollen count larger than or equal to 10 grains/m ³ .
Stop date of EGPS	The last day of the last occurrence of 3 consecutive days with (non-missing) pollen count lager or equal to 10 grains/m ^{3.}
PGPS	The 14 consecutive days period with the highest average pollen count during the entire grass pollen season.

Table 10 Grass pollen season definitions.

Based on the definition above, if the EGPS is shorter than 14 days, than PGPS will be equal to EGPS. In addition, a visual inspection of the pollen count (pollen grains/m3 versus time) will be made to validate the pollen counts in the season.

In case of missing pollen counts for specific pollen regions the 3 following principals will be used prior to unblinding:

• If pollen counts for maximum 2 days will be missing with at least 5 days with observed pollen counts days then the missing pollen counts (after first occurrence of pollen) will be replaced by applying the last observation carried forward method.

- If pollen counts will be completely missing or missing for extended period of time for a specific pollen station then a replacement pollen station will be manually assigned.
- In all other cases of missing pollen counts start and stop dates will be defined by visual inspection of the pollen counts for the specific pollen station and neighbouring pollen stations to approximate the general approach specified above.

Pollen seasons (i.e., actual start and end dates or start and end dates based on visual inspection) will be defined prior to database lock and further specified in Appendix B: pollen seasons start and stop dates.

9.2 Derivation of endpoints

Symptoms and medication use days was recorded daily by the subject in the eDiary. For each day it was only possible for the subject to either record both symptoms and medication use or neither.

9.2.1 DSS

The 6 symptoms of rhinoconjunctivitis consists of 4 rhinitis symptoms (runny nose, blocked nose, sneezing, itchy nose) and 2 conjunctivitis symptoms (gritty feeling/red/itchy eyes, watery eyes). Each symptom is scored from 0 to 3 by the subject daily: 0 = no symptoms, 1 = mild symptoms, 2=moderate symptoms, and 3=severe symptoms.

The DSS is the sum of the 6 individual DSS and ranges from 0 to 18.

9.2.2 DMS

The DMS is the sum of the total daily scores for each medication. The total DMS for each symptomatic medication is calculated as the unit score multiplied by the number of units entered in the daily diary by the subject (Table 11). Note that the score is capped so that for each medication the score of the recommended dose is also the maximum score, i.e. this score cannot be exceeded even though the recommended dose is exceeded. The DMS ranges from 0 to 20.

Table 1	1 Symptom	relievina	medication	for rhinitis	with/without	coniunctivitis

Symptom-relieving medication	Score/dose unit	Maximum daily score	SUGGEST: MAX DAILY UNITS
Desloratadine tablets, 5 mg	6	6	1 (Tablets)
Olopatadine eye drops, 1 mg/mL	1.5 pr. eye	6	4 (Drops)
Mometasone nasal spray, 50 µg/dose	2	8	4 (Puffs)
Maximum daily rhinitis and/or conjunctivitis medication score	-	20	

Date: 27-Oct-2023 Version: 1.0 Status: Final Page: 36 of 47

9.2.3 TCS

The daily TCS is the sum of the DSS and the DMS and ranges from 0 to 38.

9.2.4 RQLQ

The RQLQ has 28 questions in 7 domains (activity limitation, sleep problems, nose symptoms, eye symptoms, non-nose/eye symptoms, practical problems and emotional function) (Juniper et. al 1998).

Subjects were asked how bothered they have been by their rhinoconjunctivitis during the previous week and to respond to each of the 28 questions on a 7-point scale (from 0 = not bothered/none of the time to 6 = extremely bothered/all of the time). The overall RQLQ score is the mean of all 28 responses and the individual domain scores are the means of the items in those domains.

		1

9.3 Derivation of average endpoints

Average endpoints will be calculated for both EGPS and PGPS pollen seasons. Pollen seasons are defined above, and the average endpoints will be derived for the following endpoints:

- TCS
- RQLQ
- DSS
- DMS

Average endpoints will be derived as the simple mean of all observations (i.e. non-missing daily/weekly values) within the relevant time frame and data point set.

9.4 Imputation of dates

9.4.1 Partial dates in AE reporting

Partial dates and time for start of AEs will be imputed as follows:

- Missing day will be imputed as maximum of first day of month and day of first IMP dose.
- Missing month will be imputed as maximum of first day in January and date of first IMP.
- Missing time is calculated as the first minute of the day (i.e. if the AE start date is 16-AUG-2022 then the AE start datetime will be 16-AUG-2022 T:00:00)

Partial dates and time for end of AEs will be imputed as follows:

- Missing day will be imputed as minimum of last day in month and day of last contact.
- Missing month will be imputed as minimum last day of December and date of last contact.
- Missing time is calculated as the last minute of the day (i.e. if the AE end date is 16-AUG-2022 then the AE start datetime will be 16-AUG-2022 T:23:59)

With these imputation rules, AEs will be considered TE when dates are partial and the existing information does not exclude the possibility of the event being treatment-emergent.

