9.2 Precautions in relation to first dosing

The first intake of IMP should be at the clinic with a subsequent 30 minutes observation period. An oropharyngeal examination should be performed prior to the first IMP dosing and should be repeated after 30 minutes.

For subjects with severe oral inflammation (e.g. oral lichen planus, mouth ulcers or thrush), oral wounds or following oral surgery, including dental extraction or following tooth loss, initiation of IMP treatment should be postponed to allow healing of the oral cavity.

For subjects with symptoms of or in treatment for upper respiratory tract infection, acute sinusitis, acute otitis media or other relevant infections, initiation of IMP treatment should be postponed until the condition has improved. If first dosing is postponed, the first intake of IMP should still be at the clinic with a subsequent 30 minutes observation period.

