Primary trial completion date	Date of the last data collection for the primary endpoint (ClinicalTrials.gov) is the last scheduled physical visit for any subject (V9).
Rescue medication	Medicinal products provided by ALK when the efficacy of the IMP is not sufficient or likely to cause an AE to the subject or to manage an emergency situation in relation to grass pollen allergy symptoms in agreement with the EMA Definition of IMPs and Use of AMPs Consultation Document (EMA 2016)
	The rhinoconjunctivitis rescue medication in this trial is:
	Antihistamine tablets
	Antihistamine eye drops
	Corticosteroid nasal spray.
Source documents	Source documents are original documents, data, and records from which the subjects' electronic case report form (eCRF) data are obtained. These include, but are not limited to, hospital records (from which medical history and

	concomitant medication may be summarised into the eCRF), clinical and office charts, laboratory and pharmacy records, diaries, microfiches, radiographs, and correspondence.
Systemic corticosteroids	Oral, intramuscular, or intravenously administered corticosteroids.
TEAE	TEAEs are defined as AEs with start date and/or time on or after the time of first IMP administration and no later than 7 days after last IMP administration.
Trial completion	The trial is completed once the CSR is signed.
Withdrawal from trial date	Date of subject withdrawal from trial. In case of subjects lost to follow-up, the withdrawal date is defined as the date the investigator/sponsor decides to withdrawal the subject.

3 Introduction

The SAP supplements the statistical section in the protocol and provides additional details regarding estimands, analysis sets, endpoints and statistical analyses. In Section 9.1 detailed descriptions of pollen seasons, derivation of endpoints, imputation of dates, and the statistical analyses are provided. In supplementary document to the SAP: Documentation of Trial Analysis Sets, the various subject related listings are provided.

Changes to the analyses and changes that might (or can) impact the analyses described in the protocol are documented in Section 6.5.

This SAP has been written and approved before database lock and unblinding.

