6.4.2.1 Events of special interest

An AE is any untoward medical occurrence in a subject that does not necessarily have a causal relationship with the administered IMP. An AE is a TEAE if the time of onset is on or after the time of the first dose administration of IMP and, no later than seven days seven days after the last dose administration of IMP. Selected (non-serious or serious) AEs are considered ESIs. ESIs are events that are considered critical for the evaluation of the product's safety profile and for which additional data was collected. ESIs for this trial are:

- Systemic allergic reactions including anaphylaxis
- Events treated with adrenaline
- Severe local swelling of the mouth and/or throat
- Eosinophilic oesophagitis.

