6.4.2.2 Reporting of adverse events

All TEAEs will be summarised by treatment group according to causality (IMP related or not), severity (mild, moderate, severe), seriousness (yes/no), action taken, outcome (recovered or resolved / recovered or resolved with sequelae / not recovered or not / resolved / fatal / unknown), and whether the event led to IMP discontinuation and interruption. The number of subjects in treatment group, the frequency and proportion of subjects having the event, as well as the number of events and proportion of events will be displayed. A similar summary table will be produced for all IMP-related TEAEs.

All TEAEs and all IMP-related TEAEs will be summarised (in separate tables) by treatment group, SOC, and PT, displaying number of subjects in treatment group, and number and frequency of subjects having the event. The tables will be sorted according to most frequent SOC and PT in the active treatment group, and the most common TEAEs defined as those that are present in at least 2% of subjects in the active treatment group will be marked.

Severe TEAEs will be listed only if there are fewer than 10 events in total. Otherwise, severe TEAEs will also be summarised and presented by SOC and PT similar to how TEAEs are presented. The same follows for SAEs, TEAEs leading to IMP discontinuation, and IMP-related TEAEs leading to IMP interruption.

For most frequent IMP-related TEAEs (present in at least 2% of subject in the active treatment group) onset and duration will be presented as follows: time to onset and average duration both in days, will be presented by SOC and PT and treatment. In addition, for day 1 of treatment average time to onset in minutes will be presented by SOC PT and treatment.

In addition, most frequent non-serious TEAEs reported in at least 5% of subjects in any treatment group by SOC and PT.

For the most frequent IMP-related TEAEs which are recurrent, the average daily duration and the average duration in days from first to last occurrence will be presented by PT and treatment.

A table with the overall summary of the safety profile will be produced showing number of subjects with TEAEs, IMP-related TEAEs, IMP-related severe TEAEs, IMP-related treatmentemergent SAEs, IMP-related TEAEs leading to IMP discontinuation and each type of IMPrelated treatment-emergent ESI by treatment group.

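### SAP 9.4.1 and 9.4.3: a midnight start time conflicts with the time-based TEAE test, the first-dose floor ignores known end dates, and a partial end date makes an on-trial drug 'previous'

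*SAP*

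**What the plan says.** **Start time.** SAP 9.4.1: "Missing time is calculated as the first minute of the day". Its own example is a datetime at 00:00.

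**Start day and month.** For an unknown start day, SAP 9.4.1 has "Missing day will be imputed as maximum of first day of month and day of first IMP dose". The parallel rule for an unknown start month reads "Missing month will be imputed as maximum of first day in January and date of first IMP". Neither rule takes the event's end date as an input.

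**Intended result.** 9.4.1 closes by saying that, under these rules, "AEs will be considered TE when dates are partial and the existing information does not exclude the possibility of the event being treatment-emergent".

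**TEAE test.** SAP 6.4.2.1: "An AE is a TEAE if the time of onset is on or after the time of the first dose administration of IMP". SAP section 2 is looser: "TEAEs are defined as AEs with start date and/or time on or after the time of first IMP administration".

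**First dose.** Protocol 9.2: "The first intake of IMP should be at the clinic with a subsequent 30 minutes observation period".

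**Output that uses the time.** SAP 6.4.2.2, for IMP-related TEAEs seen in at least 2% of active subjects: "for day 1 of treatment average time to onset in minutes will be presented by SOC PT and treatment".

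**Medication.** SAP 9.4.3 imputes no medication dates and treats every drug with a partial end date as previous. SAP section 2 defines concomitant medication as anything continued at trial entry or added during the trial.

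**The concern.** The floor at first dose exists so that a possibly treatment-emergent event is not lost because its date is incomplete. Setting the time to midnight undoes this on the one date where it matters: the floor brings the event to the dose date, and the time rule then puts it hours before the dose. Two programmers following different sentences of the SAP could get different TEAE counts from the same data. The ambiguity falls on the supervised first dose, where onset timing is of most interest, and TEAEs are named supportive secondary endpoints in SAP 3.1.

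The other two faults are simpler. A start later than the event's own end is an invalid record. A drug known to have been taken on trial but labelled previous contradicts the SAP's own definition.

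**Working it through.** The plan states no figure to reproduce beyond its example, where an untimed 16-Aug-2022 becomes 00:00 on that date. The rules applied literally return the same value.

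**1. Start time against the TEAE test.** Clock time of dosing is not in the documents. Assume a first dose on 15-Sep-2021 at 10:00.

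| Recorded start | Imputed start | Minutes from dose | Time test (6.4.2.1) | Date test (one reading of section 2) |
|---|---|---|---|---|
| 15-Sep-2021, no time | 15-Sep 00:00 | −600 | not TE | TE |
| Sep 2021 | 15-Sep 00:00 | −600 | not TE | TE |
| 2021 | 15-Sep 00:00 | −600 | not TE | TE |
| 16-Sep-2021, no time | 16-Sep 00:00 | +840 | TE | TE |
| Oct 2021 | 01-Oct 00:00 | +22,440 | TE | TE |

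The first three rows fail the time test for any dose time after 00:00. Dosing at 07:00 gives −420 minutes and at 18:00 gives −1080. The problem is confined to the first-dose date.

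**How often could such an event be treatment-emergent?** Inputs: randomisation from the start of August 2021 (protocol flow chart, footnote 1, taken as the start of the window) to 31-Dec-2021 (SAP 3.2.2), and first visit of the first subject on 02-May-2021 (SAP 3.2.2). SAP 3.2 gives 15-Aug-2022 for the first randomisation. That is later than the last randomisation, so it is not used. Postponed first doses are ignored. Possible first-dose dates: 31 + 30 + 31 + 30 + 31 = 153.

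- Day missing, in the first-dose month: with dose day d in a month of N days, the share of possible onset dates on or after the dose date is (N − d + 1)/N. Minimum 1/31 = 3.2%; maximum 100%. The monthly sums are (N + 1)/2, so the mean is (16 + 15.5 + 16 + 15.5 + 16)/153 = 79/153 = 51.6%. This assumes consent before that month began.
- Month missing, year 2021: onset can be recorded only from consent, so there are at most 244 possible days (02-May to 31-Dec-2021). The share is k/244 for k = 1 to 153: minimum 0.4%, maximum 153/244 = 62.7%, mean 77/244 = 31.6%.

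These are shares of calendar dates, not of events. In all these cases the closing sentence of 9.4.1 makes the event TE unless other information excludes it, while the literal time test makes none of the untimed ones TE.

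**Day-1 onset table.** On the date reading or the closing sentence, the event is kept but its start stays at 00:00. Protocol 12.3 gives mouth itching lasting 5 to 10 minutes after intake as its example. Taking 10 minutes as an onset time for scale, one value of −600 cancels 600/10 = 60 real onsets. The SAP does not say that imputed times are left out.

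**2. Floor against a known end.** First dose 15-Aug-2021, event start Aug 2021, known end 10-Aug-2021. The start becomes the later of 01-Aug and 15-Aug, which is 15-Aug-2021, 5 days after the end. The result is the same whether the day rule compares calendar dates or only days of the month. Protocol 12 collects events from consent, so such records can exist.

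**3. Medication label.** A drug starts in March 2022 and its end is recorded as July 2022. Its earliest possible end is 01-Jul-2022, and the last subject was randomised on 31-Dec-2021. For any subject still in the trial in March 2022 it was taken on trial. SAP 9.4.3 calls it previous; SAP section 2 makes it concomitant.

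**The case against.** The best defence is the closing sentence of 9.4.1. Read as an overriding rule, it keeps every floored event in the TEAE count and lets a known end before dosing exclude an event. SAP section 2 separately allows a date comparison, which rescues a complete first-dose date that lacks only a time. A reader might therefore infer too much in three places:

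- That untimed first-dose-day events are certainly lost as TEAEs. The documents show a conflict between rules, not a settled loss.
- That events known to have ended before dosing will be counted as treatment-emergent. The closing sentence should prevent that. What remains under part 2 is the invalid imputed date.
- That 9.4.3 mislabels on-trial drugs in general. Its rule covers only drugs with a partial end date.

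What the defence does not settle is precedence. The closing sentence presents inclusion as the result of the imputation rules, and under 6.4.2.1 they do not give that result. It speaks of partial dates, so it is unclear whether it covers a missing time alone. It also does nothing about the 00:00 value in the minutes table. Nothing in the SAP rescues 9.4.3.

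The case for small impact also stands. The minutes table covers only the more frequent related events, and SAP 8.7 does not say that prior and concomitant drugs are tabulated separately.

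**Conclusion.** The rules are wrong as written and should be corrected, with limited consequences. Under 6.4.2.1, every untimed event dated on or floored to the first-dose date fails the TEAE test, against the SAP's stated intent, and the SAP does not say which rule prevails. The floor can create a start after a known end. The label in 9.4.3 contradicts the SAP's definition of concomitant medication.

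The number of affected records is unknown, because the documents do not say how many events lack a time, day or month, or how many drugs have partial end dates. Efficacy is untouched. Only descriptive safety and medication output can change, and SAP 6.4.2.2 still lists non-treatment-emergent events. The negative-minute range rests on assumed clinic hours; the failure of the time test needs only a first dose after midnight.

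**What to change.** (a) State one TEAE comparison, in the same words, in SAP section 2 and 6.4.2.1. Say that the closing sentence of 9.4.1 governs both partial dates and missing times. When the start date (recorded or imputed) is the first-dose date and the time is missing, set it to the time of first intake, unless a known end precedes that intake. Leave imputed times out of the day-1 minutes table.

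(b) Apply the first-dose floor only when the known month (or the known year, if the month is missing) contains the first dose and the latest possible end is not before first dose. Otherwise use the first day of the known month or year, but not earlier than the consent date and not later than a known end date. The consent limit is needed because 01-Jan-2021 would precede any subject's first visit.

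(c) Class a drug with a partial end date as previous only if its latest possible end is before trial entry; otherwise class it as concomitant. Define the entry date. Protocol 4.3 treats consented screen failures as not entered, whereas protocol 15.3 counts them among subjects who entered, and SAP 5.1 defines the same set by signed consent.

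Cost: a few sentences in SAP section 2, 6.4.2.1, 9.4.1 and 9.4.3, and a small programming change, best made before database lock and unblinding. No new data are needed.

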9.4.2 Incomplete date for last IMP dose

Any partial date of last dose will be imputed as follows:

- Missing day is imputed as minimum of last day in month and day of last visit.
- Missing month is imputed as minimum of last day of December and date of last visit.
- Missing last IMP dose date is imputed as the date of last known visit

